9.3. Sample Size Determination

The sample sizes planned for the study arise from logistic feasibility and past experience with first in human (FIH) studies in oncology and are not driven by statistical considerations. It is expected that approximately 270 patients will be required (including dose escalation and expansion cohorts of Portion A and Portion B).

Due to the dynamic nature of the Bayesian allocation procedure, the sample size of the TITE-CRM approach can not be determined in advance. The maximum sample size is set as 45 in order to have a reliable and accurate estimate of the MTD based on simulation results. Based on probability theory, a sample size of 45 will ensure the estimates of any binary variable (eg, objective response rate) have a 95% confidence interval of width <0.30. A sample size of 45 also enables us to detect any unexpected toxicity that occurs at 5% rate (in a non-dose-dependent fashion) with a probability of 0.90, and that occurs at 10% rate with a probability of 0.99.

A stopping rule ([Section 3.3.2](#)) will also be implemented for possible early stopping if there is strong confidence in the estimated MTD.

Portion A expansion cohorts include patients with solid tumors of interest who progressed after treatment with an immune checkpoint inhibitor (anti-CTLA-4, anti-PD-1/PD-L1). The target sample size is approximately 20 patients with advanced melanoma at each tested dose (0.24 mg/kg, 0.6 mg/kg, 1.2 mg/kg) and approximately 20 patients, including other tumor types as described in [Section 4.1, Inclusion Criteria](#) (Criterion 1). With 20 patients with advanced melanoma, the maximum standard error of the objective response rate (ORR) is 0.11.

Number of Patients with Responses/Sample Size (Advanced Melanoma)	Objective Response Rate (ORR) and Estimated 95% CI (%)*
2/20	10% (1.2, 31.7)
4/20	20% (5.7, 43.74)
6/20	33% (11.9, 54.3)
10/20	50% (27.2, 72.8)

*Clopper-Pearson CI

Portion B expansion cohorts include approximately 100 patients with FL refractory to rituximab (see [Section 4.1](#) for definition of FL disease refractory to rituximab) with 80 patients treated at the selected RP2D (1.2 mg/kg or 0.24 mg/kg) dose level of PF-05082566. With 80 patients, the maximum standard error of the ORR is 0.06.

Responses/Sample size (FL Refractory to Rituximab)	Objective Response Rate (ORR) and Estimated 95% CI (%)*
40/80	50% (38.6, 61.4)
44/80	55% (43.5, 66.2)
48/80	60% (48.4, 70.8)
56/80	70% (58.7, 79.7)

*Clopper-Pearson CI

9.4. Efficacy Analysis

In this first-in-human study anti-tumor activity is a secondary objective in the dose escalation cohorts and a primary objective in the expansion cohorts and will be evaluated separately in Portion A and Portion B.

The detailed definitions of objective response (OR), best overall response (BOR), objective ORR, duration of response (DR), time to tumor response (TTR), progression-free survival (PFS), and overall survival (OS) will be provided in a Statistical Analysis Plan (SAP).

Tumor Response will be presented in the form of patient data listings that include, but are not limited to, tumor type, received (maximum) dose, overall tumor response at each visit, and best overall response. In addition, progression date, death date, date of first response and last tumor assessment date will be listed, together with Duration of Response, Progression Free Survival and Overall Survival. If any responses are observed for patients with measurable disease at baseline, tumor responses will be tabulated by dose level(s).

ORR by treatment group will be calculated along with the two-sided 95% CI using the Clopper-Pearson method.

DR, PFS, and OS will be analysed using Kaplan-Meier methods and descriptive statistics. Point estimates will be presented with their 95% confidence intervals.

TTR will be summarized using simple descriptive statistics (eg median and range).

CCI

9.5. Analysis of Other Endpoints

9.5.1. Analysis of Pharmacokinetics

9.5.1.1. Single- and Multiple-Dose PF-05082566 and Rituximab PK Analysis

Standard serum PK parameters including the maximum serum concentration (C_{max}), time to maximum serum concentration (T_{max}), and area under the serum concentration versus time curve (AUC) for PF-05082566 will be estimated using non-compartmental analysis, as data permits. If data permit or if considered appropriate, minimum serum concentration (C_{min}), average serum concentration (C_{ave}), pre-dose serum concentration during multiple dosing (C_{trough}), area under the serum concentration versus time curve from 0 to infinity (AUC_{inf}), area under the serum concentration versus time curve over dosing interval (AUC_{tau}), terminal elimination half-life ($t_{1/2}$), total systemic clearance (CL), steady state volume of distribution (V_{ss}), accumulation ratio (Rac) will be estimated. For rituximab, C_{max} and C_{trough} will be summarized. Descriptive statistics will be provided for these PK parameters in tabular form (n, mean, SD, CV, median, minimum, maximum, geometric mean and its associated CV) by dose, cycle and day.

For PF-05082566 and rituximab concentrations, individual values and descriptive statistics (n, mean, SD, CV, median, minimum, maximum, geometric mean and its associated CV) will be presented by dose, cycle, day of assessment, and nominal time in tabular form. Individual patient and median profiles of the concentration-time data will be plotted by dose, cycle and day. Median profiles will be presented on both linear-linear and log-linear scales. AUC_{inf} (AUC_{tau} at steady state), AUC_{last} and C_{max} for PF-05082566 may be plotted against dose (using a logarithmic scale). These plots will include individual patient values and the geometric means for each dose. These plots will be used to help understand the dose proportionality for PF-05082566.

CCI

9.5.1.3. Analysis of Immunogenicity Data

For the immunogenicity data, the percentage of patients with positive ADA and neutralizing antibodies (Nab) will be summarized by dose. For patients with positive ADA, the magnitude (titer), time of onset, and duration of ADA response will also be described, if data permit. The effect of ADA/Nab on PF-05082566 PK and safety will be evaluated if data permit.

CCI [Redacted]

[Redacted]

[Redacted]

[Redacted]

CCI [Redacted]

[Redacted]

[Redacted]

CCI [Redacted]

[Redacted]

[Redacted]

[Redacted]

[Redacted]

[Redacted]

C [REDACTED]
C [REDACTED]
I [REDACTED]
I [REDACTED]
[REDACTED]
I [REDACTED]
I [REDACTED]
[REDACTED]
CCI [REDACTED]
[REDACTED]

9.6. Safety Analysis

Summaries and analyses of the primary safety endpoint(2-cycle DLT) in the dose escalation cohorts will be based on the per protocol analysis set. DLT will continue to be monitored as a secondary endpoint in the expansion cohorts based on the per protocol analysis set. Summaries and analyses of all other safety parameters will include all patients in the safety analysis set.

9.6.1. Analysis of Primary Endpoint in the Dose Escalation Cohorts

First 2 cycles DLTs is the primary endpoint of the dose-escalation component of the study. The occurrence of DLTs observed in the dosing cohorts is used to estimate the MTDs of PF-05082566 with or without rituximab as described in [Section 4.4](#). AEs constituting DLTs will be listed per dose level.

9.6.2. Analysis of Secondary Safety Endpoints

Adverse Events

AEs will be graded by the investigator according to the CTCAE version 4.03 and coded using the Medical Dictionary for Regulatory Activities (MedDRA). The focus of AE summaries will be on Treatment Emergent Adverse Events, those with initial onset or increasing in severity after the first dose of study medication. The number and percentage of patients who experienced any AE, SAE, treatment related AE, and treatment related SAE will be summarized according to worst toxicity grades. The summaries will present AEs both on the entire study period and by cycle (Cycle 1 and Cycles ≥ 1).

Laboratory Tests Abnormalities

The number and percentage of patients who experience laboratory test abnormalities will be summarized according to worst toxicity grade observed for each laboratory assay. The analyses will summarize laboratory tests both on the entire study period and by cycle (Cycle 1, Cycle 2, and Cycles ≥ 2).

For laboratory tests without CTCAE grade definitions, results will be categorized as normal, abnormal or not done.

Electrocardiograms

The analysis of ECG results will be based on patients in the safety analysis set with baseline and on-treatment ECG data. ECG collected prior to the first day of dosing will be considered the baseline ECG.

ECG measurements (an average of the triplicate measurements) will be used for the statistical analysis and all data presentations. Any data obtained from ECGs repeated for safety reasons after the nominal time-points will not be averaged along with the preceding triplicates. Interval measurements from repeated ECGs will be included in the outlier analysis as individual values obtained at unscheduled time points.

QT intervals will be corrected for heart rate (QTc) using standard correction factors (ie, Bazett's, Fridericia's and possibly a study specific factor). The adequacy of the correction method will be assessed graphically (plots of QT and QTc versus RR) and supplementary transformations may be considered, as appropriate. Data will be summarized and listed for QT, HR, RR, PR, QRS, QTcF and QTcB by treatment and dose. Individual QTc (all evaluated corrections) intervals will be listed by compound, time and dose. The most appropriate correction factor will be selected and used for the following analyses of central tendency and outliers and used for the study conclusions. Descriptive statistics (n, mean, median, standard deviation, minimum, and maximum) will be used to summarize the absolute QTc value and changes from baseline in QTc after treatment by compound, dose and by time point. For each patient and by treatment, the maximum change from baseline will be calculated as well as the maximum post-baseline value across time-points. Outlier analysis of the QTc data will be conducted and summarized as follows:

- The number of patients with maximum change from baseline in QTc (<30, 30-<60, and ≥ 60 msec);
- The number of patients with maximum post-dose (post-baseline) QTc (≤ 450 , $>450-\leq 480$, $>480-\leq 500$, and >500 msec).

Shift tables will be provided for baseline vs. worst on study QTc (one or more correction method will be used) using Maximum CTCAE Grade. As well as tables of ECG abnormality at baseline (yes, no, not done: (n, %)). Patients experiencing clinically-relevant morphological ECG changes will be summarized (including frequency and percentage).

The effect of drug concentrations on QTc change from baseline will be explored graphically. Additional concentration-QTc analyses may be performed. Data may be pooled with other study results and/or explored further with PK^{CCI} models.

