9. Triplicate 12-Lead electrocardiogram (ECG): At each time point, 3 consecutive 12-lead ECGs will be performed approximately 2 minutes apart to determine mean QTc. When coinciding with blood sample draws for PK, ECG assessment should be performed prior to blood sample collection, such that the blood sample is collected at the nominal time. ECGs will be collected as follows: a) at Screening; b) On Cycle 1 Day 1 (C1D1), at pre-dose, 1.5 hr post start of infusion and 24 hrs post-dose; c) On Cycle 1/ Days 8 and 15; d) On Cycles ≥ 2 Day 1, at 1.5 hr post start of infusion f) at End of Treatment. If the mean QTc interval is prolonged (>500 msec corrected by Fridericia's formula), then the ECGs should be re-evaluated by a qualified person at the center for confirmation. Additional triplicate ECGs may be performed as clinically indicated.
10. Hematology: No need to repeat on C1D1 if the screening assessment is performed within 7 days prior to that date. To be performed weekly. If during the first 2 cycles of treatment a grade 4 hematologic event is evident, the hematology assessment should be repeated at least every other day to assess for events qualifying as DLT. See [Table 8](#) for Laboratory Tests list.
11. Blood Chemistry: No need to repeat on C1D1 if the screening assessment is performed within 7 days prior to that date. To be performed weekly. See [Table 8](#) for Laboratory Tests list.
12. Coagulation: No need to repeat on C1D1 if the screening assessment is performed within 7 days prior to that date. To be performed weekly for Cycle 1 and on Day 1 for all remaining cycles. See [Table 8](#) for Laboratory Tests list.
13. Urinalysis: Dipstick is acceptable. Microscopic analyses if dipstick is abnormal. No need to repeat on C1D1 if the screening assessment is performed within 7 days prior to that date. To be performed at baseline and end of treatment. See [Table 8](#) for Laboratory Tests list.

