30. Follow up period: Patients should be evaluated for serious adverse events up to 60 days after last dose of study treatment. Patients continuing to experience toxicity at this point will continue to be followed at least every 4 weeks until resolution or determination, in the clinical judgment of the Investigator, that no further improvement is expected. Immunogenicity (ADA) samples should be collected beyond 28 days for patients who are positive for ADA (Refer to Footnote 27). During the follow-up phase, Immunogenicity (ADA) samples should be collected at the same time as disease assessments are being performed until ADA levels return to baseline or until the patient enters the survival follow phase. Thereafter, patients whose disease has not progressed at the end of treatment will enter into disease follow-up. During this follow-up period, patients will have disease assessments performed every 16 weeks (± 1 week). Once patients have exhibited disease progression, they will enter into survival follow-up for assessment of survival only. A new anti-cancer therapy will be reported on the CRF. Follow-up for survival will be conducted every 12 weeks (± 4 weeks) for up to 2 years from first dose of study treatment for the last enrolled patient (telephone calls acceptable).
31. For patients continuing on study beyond 8 cycles of therapy, continued treatment will be on a reduced visit schedule (Day 1 of each cycle), or as clinically indicated, until disease progression, loss of clinical benefit, unacceptable toxicity, or withdrawal of consent up to a maximum of 2 years from the first dose of study drug.

CCI

Table 3. Schedule of Activities: Portion B (PF-05082566 + Rituximab) Assessments (Dose Escalation Only)

Protocol Activity (Cycle Day relative to PF-05082566 dosing)	Screen ¹	CYCLE 1						CYCLE ≥2-8 ³⁵				>Cycle 8 ^{23,26,35}	End of Treatment ³²	Follow up ³³
	Within 28 days prior to enrollment	Day (-7) ³⁴	Day (0)	Day 1	Day 7	Day 14	Day 22	Day 1 (± 2)	Day 8 (± 2)	Day 15 (± 2)	Day 22 (± 2)	Day 1 (± 2)		
Visit Window														
Informed Consent ²	X													
Tumor History ³	X													
Medical History ⁴	X													
Physical Examination ⁵	X	X		X				X				X	X	
ECOG Performance Status ⁶	X	X		X				X					X	
Baseline Signs and Symptoms ⁷	X													
Vital Signs (BP, pulse, and body temperature) ⁸	X	X	X	X	X	X	X	X				X	X	
Safety Labs/Measurements														
12-Lead ECG ⁹	X	X		X		X		X				X	X	
Hematology ¹⁰	X	X	X	X	X	X	X	X	X	X	X	X	X	

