11. Triplicate 12 Lead ECG: At each time point, 3 consecutive 12 lead ECGs will be performed approximately 2 minutes apart to determine mean QTc. When coinciding with blood sample draws for PK, ECG assessment should be performed prior to blood sample collection, such that the blood sample is collected at the nominal time. ECGs will be collected as follows: a) at Screening; b) On Day -7, prior to the dose of Rituximab and at end of infusion (Portion B only); c) On Cycle 1 Day 1 (C1D1), prior to the dose of PF-05082566 and 1.5 hours post start of infusion; d) On Cycle 2-4 Day 1 at 1.5 hours post start of infusion; and e) at End of Treatment. Additional triplicate ECGs may be performed as clinically indicated. If the QTc interval is prolonged (>500 msec by any correction method), then the ECGs should be re-evaluated by a qualified person at the center for confirmation. A subset of approximately 30 FL patients enrolled at selected sites in the FL-3 expansion cohort of Portion B will be assessed using an ECG machine provided by central vendor to allow central review of ECG.
12. Hematology and Chemistry: No need to repeat on C1D1 for Portion A or Cycle 1 Day -7 [C1D(-7)] for Portion B if the screening assessment is performed within 7 days prior to that date. To be performed weekly only for portion B patients during Cycle 1, and on Day 1 for all subsequent cycles. See [Table 8](#) for Laboratory Tests list.
13. Coagulation: No need to repeat on C1D1 (Portion A) or C1D(-7) (Portion B) if the screening assessment is performed within 7 days prior to that date. To be performed weekly only for portion B patients during Cycle 1, and on Day 1 of all subsequent cycles. See [Table 8](#) for Laboratory Tests list.

14. Urinalysis: Dipstick is acceptable. Microscopic analyses if dipstick abnormal. No need to repeat on C1D1 (Portion A) if the screening assessment is performed within 7 days prior to that date. To be performed at screening, Cycle 1 Day 1, and at the end of treatment. See [Table 8](#) for Laboratory Tests list.

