SAFETY LABORATORY REQUIREMENTS	
- May be performed up to 48 hours prior to scheduled cycle Day 1 visits to facilitate availability of results to the investigator at the time of the clinic visit.	
Assessments	
Hematology Panel:	Chemistry Panel:
Absolute Neutrophil Count	Sodium
Hemoglobin	Potassium
	Calcium
Platelet Count	Creatinine
WBC with differential (5-part if available)	Albumin
	Alanine aminotransferase (ALT)
	Aspartate aminotransferase (AST)
	Glucose
	Phosphorus
	Magnesium
	Bilirubin: total
	Blood urea nitrogen (BUN)
	Alkaline phosphatase
	Lactate dehydrogenase (LDH)
	Total protein
	Uric acid (or urate)
Coagulation Panel: international normalized ratio (INR) or prothrombin time (PT), Partial thromboplastin time (PTT)	Hepatitis Screening: hepatitis B surface antigen and core antibody; anti-hepatitis C antibody.

Table 8 Safety Laboratory Tests

SAFETY LABORATORY REQUIREMENTS	
- May be performed up to 48 hours prior to scheduled cycle Day 1 visits to facilitate availability of results to the investigator at the time of the clinic visit.	
Assessments	
Urinalysis: measurement of pH, specific gravity, protein/albumin, glucose, blood/hemoglobin, ketones/acetone, Urine dipstick for urine protein: if positive collect 24-hr and microscopic (Reflex Testing), Urine dipstick for urine blood: if positive collect a microscopic (Reflex Testing). No need to repeat on C1D1 if baseline assessment performed within 7 days prior to that date. Pregnancy Test (serum or urine): Conducted for women of childbearing potential only.	Endocrine Function Assessments: baseline assessments including but not limited to: TSH, Free T4. In the presence of clinical suspicion of hypopituitarism or hypoadrenalism, laboratory testing should include one or more of the following: TSH, ACTH, and cortisol levels before and 30-60 minutes after corticotropin stimulation.

TABLE OF CONTENTS

LIST OF TABLES	53
LIST OF FIGURES	53
APPENDICES	54
1. INTRODUCTION	55
1.1. Mechanism of Action/Indication.....	55
1.2. Background and Rationale	55
1.2.1. Scientific Rationale: Target Biology and Mechanism of Action.....	55
1.2.2. Pre-Clinical Development of PF-05082566	56
1.2.2.1. In Vitro Data.....	56
1.2.2.2. In Vivo Data: Functional Activity of PF-05082566.....	57
1.2.2.3. Anti-Tumor Activity of PF-05082566	58
1.2.2.4. Combination Studies	58
CCI	
CCI	
CCI	
CCI	
1.4. Study Rationale	62
1.5. Summary of Benefit/Risk Assessment.....	63
2. STUDY OBJECTIVES AND ENDPOINTS.....	64
2.1. Objectives.....	64

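### Protocol 9.6.2 sets by-cycle safety windows that overlap, and in the expansion cohorts the laboratory columns can differ through the sampling schedule alone

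*Protocol*

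**What the plan says.** Protocol 9.6.2 splits the AE summaries as follows: "The summaries will present AEs both on the entire study period and by cycle (Cycle 1 and Cycles ≥ 1". For laboratory abnormalities it says: "The analyses will summarize laboratory tests both on the entire study period and by cycle (Cycle 1, Cycle 2, and Cycles ≥ 2". Timing is a named attribute of both AEs and laboratory abnormalities in the safety endpoints (Protocol 2.2.2 and 2.2.5; SAP 3.2.1 and 3.5.1).

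For the expansion cohorts, Table 5 footnote 12 sets haematology and chemistry thus: "To be performed weekly only for portion B patients during Cycle 1, and on Day 1 for all subsequent cycles". The same footnote lets Portion A skip the Cycle 1 Day 1 (C1D1) draw "if the screening assessment is performed within 7 days prior to that date". In Table 5 the Day -7, 0, 7 and 14 columns are Portion B only. For Portion A escalation, Table 1 footnote 11 reads: "Blood Chemistry: No need to repeat on C1D1 if the screening assessment is performed within 7 days prior to that date. To be performed weekly". After Cycle 8, footnote 31 says "continued treatment will be on a reduced visit schedule (Day 1 of each cycle), or as clinically indicated". Table 8 adds that safety laboratory tests "May be performed up to 48 hours prior to scheduled cycle Day 1 visits".

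The SAP summarises safety over the on-treatment period (5.2.7). Its AE table list (6.6.1.1) and laboratory grade tables (6.6.4.1) have no cycle split, and laboratory values are summarised by nominal visit. It does not say that the protocol's by-cycle tables have been dropped.

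**The concern.** A by-cycle incidence table lets a reader separate events in the first cycle from those that come later. With the printed windows it cannot do this for AEs: the only column other than Cycle 1 contains Cycle 1. The laboratory split does isolate Cycle 1 and Cycle 2, but its third column includes Cycle 2 again, so Cycles ≥3 are never shown alone.

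The laboratory table has a second problem in the expansion cohorts. The number of chances to detect an abnormality differs between cycles, and in opposite directions in the two portions. No rule says which cycle a pre-dose Day 1 result belongs to. What is at stake is the reading of early against late laboratory toxicity in the cohorts meant to support the choice of recommended Phase 2 dose. No primary endpoint, interval estimate or dose-assignment rule depends on these tables.

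**Working it through.** The plan states no figure for these tables, so there is none to reproduce. The check has four parts.

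**1. Window overlap.** Assume, for illustration only, that a patient has a 10% chance of a given AE in each cycle, independently, and is treated for 4 cycles. The probability of at least one event in m cycles is 1 − 0.9^m.

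- Cycle 1: 10.0%
- Cycles ≥1: 1 − 0.9^4 = 34.4%, identical to the whole-study column
- Cycles ≥2: 1 − 0.9^3 = 27.1%
- Cycles ≥3: 1 − 0.9^2 = 19.0%

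Subtraction does not recover the missing AE column. Overall minus Cycle 1 is 34.4 − 10.0 = 24.4%, which counts only patients whose first event came after Cycle 1. The share with any event in Cycles ≥2 is 27.1%.

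**2. Scheduled draws.** These are haematology and chemistry draws after the first dose, counted from Tables 1 and 5. Day 1 samples are taken as pre-dose, consistent with the early-draw allowance in Table 8.

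| Cohort | Cycle 1 days | Draws | Cycle 2 days | Draws |
|---|---|---|---|---|
| Portion A escalation | 8, 15, 22 | 3 | 1, 8, 15, 22 | 4 |
| Portion A expansion | none | 0 | 1 | 1 |
| Portion B expansion, from first PF-05082566 | 7, 14 | 2 | 1 | 1 |
| Portion B expansion, from first rituximab | 0, 1, 7, 14 | 4 | 1 | 1 |

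**3. What the schedule alone produces.** Let q be a constant risk that any one test is abnormal, independent between tests. With k draws, P(at least one) = 1 − (1 − q)^k. The documents give no q, so 2%, 5% and 10% are assumptions.

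| Cohort | Cycle 1 (q = 2 / 5 / 10%) | Cycle 2 |
|---|---|---|
| Portion A escalation | 5.9 / 14.3 / 27.1% | 7.8 / 18.5 / 34.4% |
| Portion A expansion | 0 / 0 / 0% | 2.0 / 5.0 / 10.0% |
| Portion B expansion, from first PF-05082566 | 4.0 / 9.8 / 19.0% | 2.0 / 5.0 / 10.0% |
| Portion B expansion, from first rituximab | 7.8 / 18.5 / 34.4% | 2.0 / 5.0 / 10.0% |

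With risk held constant, Portion A expansion rises from Cycle 1 to Cycle 2 and Portion B expansion falls. For a Portion A expansion patient treated to Cycle 8, the Cycles ≥2 column collects 7 draws: 13.2 / 30.2 / 52.2%.

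**4. Effect of moving each pre-dose Day 1 result to the cycle it closes.** C2D1 moves to Cycle 1, C3D1 to Cycle 2, and so on. Portion A expansion becomes 1 and 1 draws, and Portion A escalation 4 and 4. Portion B expansion becomes 3 (Days 7, 14 and C2D1) and 1. At q = 5% that is 1 − 0.95^3 = 14.3% against 5.0%, so the rule balances Portion A but not Portion B.

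**The case against.** The strongest reply is that the SAP may modify the protocol's plan (Protocol 9; SAP 2) and contains no by-cycle AE or laboratory toxicity table, so the flawed windows may never be used. The printed symbols may also be slips for >1 and >2. The tables are descriptive, and SAP 5.1.1 plans no hypothesis test. AE listings include every AE (SAP 6.6.1) and relevant listings show study day (5.2.4), so individual timing can be traced. Unscheduled results generally count (5.2.9), so a clinically prompted Cycle 1 test would enter a worst-grade summary. SAP 6.6.4.1 already gives laboratory values by nominal visit and uses patients evaluable for grading as the denominator over the on-treatment period.

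Most of this stands and limits the point. It does not remove it. The protocol text is operative until the SAP says otherwise. A slip still needs correcting, listings are not an incidence summary, and visit-wise values are not toxicity grades. If the SAP's silence means that the tables were dropped, timing has no by-cycle incidence table at all.

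A reader might go further and infer that any time trend in these tables is an artefact. The documents do not support that. No trend analysis is planned. AEs are recorded continuously in escalation and at each visit in expansion, not on the laboratory schedule, so only laboratory-detected AEs could be touched. Escalation sampling is close to even through Cycle 8.

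A reader might also compare weekly with 28-day sampling and infer a fourfold change in detecting a 7-day abnormality. No expansion cohort makes that switch: Portion B expansion has no draw between Day 14 and C2D1. On that model Cycle 1 detection is about 13/28 = 46% against 7/28 = 25%, or roughly 1.9-fold.

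**Conclusion.** The point holds in a limited form. Both sets of windows in Protocol 9.6.2 overlap as printed. The second AE window adds nothing to the whole-study column, and the laboratory split counts Cycle 2 twice. In expansion laboratory tables, columns can differ through the schedule alone: at q = 5%, 0% then 5.0% in Portion A, and 9.8% then 5.0% in Portion B counted from PF-05082566. These percentages are illustrative and rest on the assumed q, independence between tests, scheduled visits only, and C2D1 being booked to Cycle 2. That last assumption is open. The only cycle boundary in the SAP is in the exposure section (6.5.3), and a C2D1 sample drawn up to 48 hours early would fall in Cycle 1 under it.

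Protocol 9.2 allows the dose-finding weights to change if toxicity patterns differ between cycles, and a reader might infer that these tables could mislead that step. Nothing in the documents links them to it. This is a correction worth making to secondary descriptive tables, not a threat to the trial's main conclusions.

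**What to change.** In Protocol 9.6.2:

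- Use disjoint windows: Cycle 1 and Cycles ≥2 for AEs; Cycle 1, Cycle 2 and Cycles ≥3 for laboratory tests.
- Treat C1D1 as baseline, and assign each later pre-dose Day 1 laboratory result to the cycle it closes. This also settles the 48-hour question.
- Use as denominator the patients at risk in the window (AEs) or with a post-baseline test in it (laboratory).
- Show expansion separately from escalation in by-cycle laboratory tables. SAP treatment groups are defined by dose and regimen only (3.7.1, 5.2), so the two would otherwise share a column at common dose levels despite different sampling.

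In the SAP, state whether the by-cycle tables are kept. If they are, add them to 6.6.1.1 and 6.6.4.1 with these definitions.

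The cost is minor wording and table-shell changes, with no new data. One limit remains: Portion B expansion still has more Cycle 1 draws than later ones, so a footnote should give the scheduled draws per window. For a like-for-like view of values, the nominal-visit summaries already planned can be used.
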